8. RESEARCH QUESTION AND OBJECTIVES

The aim of this project is to evaluate the comparative effectiveness of the monovalent XBB.1.5-containing Covid-19 vaccine in preventing severe Covid-19 outcomes among individuals aged 65 years or older.

Study objectives:

- 1.** To assess the effectiveness of monovalent XBB.1.5-containing Covid-19 vaccines for the prevention of severe Covid-19 related outcomes (Covid-19 related hospitalization or Covid-19 related death).
- 2.** To assess waning of the effectiveness of monovalent XBB.1.5-containing Covid-19 vaccines for the prevention of severe Covid-19 related outcomes (Covid-19 related hospitalization or Covid-19 related death).
- 3.** To assess how the effectiveness of monovalent XBB.1.5-containing Covid-19 vaccines is affected by the coadministration with an influenza vaccine.

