	Finland	Care register for Health Care and Special Reimbursement Register. Defined as primary or secondary diagnoses registered within 2 years prior to the start of the study period.	Binary: yes/no (ICD-10 codes: C00–C43, C45–C80, C97, D05.1, D39)
	Sweden	National Patient Register. Defined as any recorded ICD-10 diagnosis during inpatient or outpatient contact and before first Covid-19 vaccination (look-back 3 years).	Binary: yes/no (ICD-10 codes: C00–C96 (without C44), D45–D47)
Comorbidity 6: Moderate to severe renal disease	Denmark	The National Patient Register. Defined as primary diagnoses regardless of type of hospital contact registered before the start date for the country-specific rollout of the fourth vaccine dose (look-back 3 years).	Binary: yes/no (ICD-10 codes: I12, I13, N00–N05, N07, N11, N14, N17–N19, Q61)
	Finland	Care register for Health Care. Defined as primary or secondary diagnoses prior to the start of the study period.	Binary: yes/no (ICD-10 codes: I12, I13, N00–N05, N07, N08, N11, N14, N18, N19, E102, E112, E142)
	Sweden	National Patient Register. Defined as any recorded ICD-10 diagnosis during inpatient or outpatient contact and before first Covid-19 vaccination (look-back 3 years).	Binary: yes/no (ICD-10 codes: I12, I13, N00–N05, N07, N11, N14, N17–N19, Q61)
Influenza vaccination status for season 2023–2024	Denmark	The Danish Vaccination Register. Defined according to the date of influenza vaccine and XBB.1.5-containing vaccine vaccinations.	Categorical (for subgroup analysis only ^d): co-administered on the same date; received influenza vaccine within 1 weeks before to 1 week after XBB.1.5-containing vaccine dose administration but no on same date; no influenza vaccine administered within 1 weeks before to 1 week after of XBB.1.5-containing vaccine dose administration.
	Finland	The National Vaccination Register. Defined according to the date of influenza vaccine (VaxigripTetra or InfluxacTetra) and XBB.1.5-containing vaccine vaccinations.	
	Sweden	The National Vaccination Register. Defined according to the date of influenza vaccine and XBB.1.5-containing vaccine vaccinations.	

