The Total Population Register [20]	The register is held by Statistics Sweden and contains data on the unique personal identifier assigned to all individuals in Sweden plus general demographic information such as date of birth, sex, country of birth, place of residence, and date of immigration and emigration.
The Cause of Death Register [21]	The register holds information on date of death and underlying as well as contributing causes of death.
The Longitudinal Integrated Database For Health Insurance And Labour Market Studies (LISA) [22]	The database is held by Statistics Sweden and holds many socioeconomic variables such as data on occupation which we used to identify whether individuals were health care personnel.
Register On Persons In Nursing Homes [23]	The register is held by the National Board of Health and Welfare and holds data on nursing care given in either nursing homes, own homes or other institutions to elderly and/or persons with physical, psychiatric or intellectual disabilities.
The National Vaccination Register [24]	The register is held by the Public Health Agency of Sweden and contains information on administered Covid-19 vaccines in Sweden including data on date of administration, the specific vaccine products, substance, formulation, batch number and dose number (for repeated doses).
Register On Surveillance Of Notifiable Communicable Diseases (Sminet) [25]	The register is held by the Public Health Agency of Sweden and contains information on notifiable diseases (for which reporting is mandatory) reported by either the analysis performing laboratories, the treating physician or autopsy performing physician, in accordance with the Swedish Communicable Diseases Act. Data included are e.g., date of disease occurrence, date of testing, date of positive test, and diagnoses.
The Swedish Patient Register [26,27]	The register is held by the National Board of Health and Welfare and comprises data on all in- and outpatient hospital specialist care in Sweden including data on dates of admission and discharge, whether hospitalization was planned or acute, codes for discharge diagnoses (recorded according to ICD-10-SE) and surgical procedures, whether discharged as deceased, to own private residence or other health care facilities, and type of department.

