9.7 Data analysis

Procedures

We will use a matched study design to evaluate the effectiveness of receiving a monovalent XBB.1.5-containing Covid-19 vaccine in comparison with not receiving a Covid-19 vaccine during the autumn and winter 2023-24. Individuals who during the study period receive an XBB.1.5-containing Covid-19 vaccine as either a fifth or sixth dose will be matched on the day of vaccination with individuals who have not yet received a fifth or sixth dose, respectively. Individuals will be matched on age (5-year bins), calendar time of last mutual vaccine dose (i.e., either 4th dose for the 5 vs 4- or 5th dose for the 6 vs 5-matched pairs), sex, region of residence, vaccination priority groups (i.e., individuals at high-risk of severe Covid-19), number of selected comorbidities (0, 1, 2, ≥ 3 of chronic pulmonary disease, cardiovascular conditions, diabetes, autoimmunity-related conditions, cancer, and moderate to severe renal disease). The day the XBB.1.5-containing Covid-19 vaccine was administered within each matched pair will serve as the index date for both individuals. If individuals who were included as a matched XBB.1.5-containing vaccine-unvaccinated individual (i.e., a reference individual) receive an XBB.1.5-containing vaccine later than the assigned index date, they will be allowed to potentially re-

enter as an XBB.1.5-containing vaccine recipient in a new matched pair on that given date and the follow-up for the current pair will be censored.

We will follow individuals from one week after the index date (to ensure full immunization among XBB.1.5-containing Covid-19 vaccine recipients) up until the day of an outcome event, end of week 18 (end of week 24 if possible) since the index date, receipt of additional Covid-19 vaccine dose, death, emigration, or end of the study period, whichever occurs first. The date of vaccination is denoted as the index date. The start of the follow-up period will commence on Day 0, corresponding to eight days after the index date. The figure below illustrates the study cohort construction, as an example of the comparison fifth vs fourth dose.

Statistical analysis

We will use 1:1 exact matching without replacement with the prespecified covariates to find a precise pairing of individuals receiving a monovalent XBB.1.5-containing Covid-19 vaccine to individuals not receiving a Covid-19 vaccine.

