Cumulative incidences will be estimated by the Aalen-Johansen estimator using death as a competing risk, and from these we will calculate the comparative VE as 1 – risk ratio at end of week 6 and 18 (or

24). The corresponding 95% CI will be calculated using the delta method. Country-specific estimates will be combined by random-effects meta-analyses implemented using the *mixmeta* package in R.

Comparative waning will be estimated using meta-regression [30]. First, we will estimate the VEs (in the specific comparison being evaluated) in each consecutive 6-week intervals (week 1-6 (day 0-42), 7-12 (day 43-84), 13-18 (day 85-126) and 19-24 (day 127-168)) by stratification on time since XBB.1.5-containing Covid-19 vaccine vaccination. Second, we will regress the VE estimates on time-since-vaccination in 6-week intervals using meta-regression in the form of an intercept and a slope coefficient. The estimated slope coefficient will represent the percentage point change in VE per 6 weeks since vaccination.

Subgroup analyses will be conducted according to sex, age groups (</≥75 years), and influenza vaccination status for XBB.1.5-containing Covid-19 vaccine vaccinated (1)co-administered on the same date, 2) received influenza vaccine within 1 weeks before to 1 week after XBB.1.5-containing vaccine dose administration but no on same date, and 3) no influenza vaccine administered within 1 weeks before to 1 week after of XBB.1.5-containing vaccine dose administration).

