We expect the majority of the study population will receive both the influenza and the XBB.1.5-containing Covid-19 vaccine on the same day, meaning that the statistical power of the subgroup analyses within populations not concurrently vaccinated will likely be lower.

Given the broad inclusion within each Nordic country, our results will likely have a high degree of generalizability to other similar populations. However, our assessment of the comparative effectiveness of monovalent XBB.1.5-containing Covid-19 mRNA-vaccines given as a fifth or sixth dose against severe Covid-19 outcomes may only indirectly support any evaluation of the effectiveness of these vaccines within other Covid-19 vaccination schedule scenarios. Our findings may similarly not directly generalize to certain subpopulations not individually studied or to populations with a

demographically different composition. Such subpopulations include for example the general population younger than 65 years old or other specific clinical subgroups that were not studied.

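### Objective 3 rests on subgroups that split XBB.1.5 recipients by influenza vaccination but leave their controls unmatched on it, so a difference between subgroups cannot be attributed to co-administration

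*Protocol*

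**What the plan says.** Protocol Section 8 lists as the third of three objectives: "To assess how the effectiveness of monovalent XBB.1.5-containing Covid-19 vaccines is affected by the coadministration with an influenza vaccine".

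The analysis for it is a subgroup analysis. Section 9.7 names sex, age group and "influenza vaccination status for XBB.1.5-containing Covid-19 vaccine vaccinated", the last in three categories: same date; within one week either side but not the same date; and "no influenza vaccine administered within 1 weeks before to 1 week after of XBB.1.5-containing vaccine dose administration". The target trial table in Section 9.1 lists the same subgroup, but its two treatment strategies are only XBB.1.5 vaccine or none. The example results table in Section 12 has one row per influenza category, each with events and person-years for both arms and its own VE.

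The covariate table in Section 9.3 sets influenza status out as "Defined according to the date of influenza vaccine and XBB.1.5-containing vaccine vaccinations" (Denmark and Sweden; Finland adds product names) and reserves it for subgroup analysis. Footnote d to that table, read literally, denies that reservation.

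The matching list in Section 9.7 begins "Individuals will be matched on age (5-year bins), calendar time of last mutual vaccine dose" and continues with sex, region, priority group and number of comorbidities. The confounder list in Section 9.3 has the same content. Influenza vaccination is in neither. For the influenza subgroups, Section 9.9 names one limitation: "the statistical power of the subgroup analyses within populations not concurrently vaccinated will likely be lower".

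**The concern.** Sex is matched exactly and age in 5-year bins, so those subgroup splits sort both members of a pair alike (for age, provided a bin boundary falls at 75). The influenza split sorts only the recipient. In the co-administered row every recipient took an influenza vaccine, and the controls are whoever happened to match. In the none-within-a-week row the recipients are selected differently, and the controls are again unselected on influenza vaccination.

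Whatever separates influenza-vaccine takers from others in risk of severe Covid-19 therefore enters each row's VE through the recipient arm. The protocol takes this kind of selection seriously elsewhere: Section 9.1 avoids comparison with never-vaccinated people because of it, and Section 9.8 names a healthy-vaccinee effect. The 21-day sensitivity analysis in 9.8 is aimed at a transient effect around the index date. It would not remove a lasting difference between takers and non-takers.

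At stake is the answer to a numbered objective. A difference between the rows could be reported as an effect of co-administration when it reflects who takes influenza vaccine.

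**Working it through.** The protocol states no expected VE or precision for Objective 3, so there is no planned figure to reproduce. The check asks what the planned rows would show if co-administration had no effect.

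**Inputs**
- From the protocol: recipients split by influenza status; controls neither matched nor split on it (9.3, 9.7); VE = 1 − risk ratio (9.7).
- Assumed, not in the protocol:
  - h, the Covid-19 risk of influenza-vaccine takers relative to non-takers within matching strata, 0.7 to 1.1.
  - p, the share of takers among controls, 0.2 in the main illustration, taken as equal across rows.
  - q, the share of takers among recipients in the none-within-a-week row, 0 or 0.5. It can exceed 0 because that row includes people vaccinated more than a week before or after.
  - The same true VE in every row, 50% in the main illustration.

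**Formulas**
- Co-administered row: VE = 1 − (1 − VE_true) × h / (1 − p + p·h)
- None-within-a-week row: VE = 1 − (1 − VE_true) × (1 − q + q·h) / (1 − p + p·h)
- Gap = (1 − VE_true)(1 − q)(1 − h) / (1 − p + p·h)

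**Main case**, h = 0.8, p = 0.2, q = 0. The denominator is 0.8 + 0.2 × 0.8 = 0.96.
- Co-administered: 1 − 0.5 × 0.8/0.96 = 58.3%
- None within a week: 1 − 0.5/0.96 = 47.9%
- Spurious gap: 10.4 percentage points

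**Varying h and q** (true VE 50%, p = 0.2)

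| h | q | Co-administered | None within a week | Gap (points) |
|---|---|---|---|---|
| 0.7 | 0 | 62.8% | 46.8% | 16.0 |
| 0.8 | 0 | 58.3% | 47.9% | 10.4 |
| 0.8 | 0.5 | 58.3% | 53.1% | 5.2 |
| 0.9 | 0 | 54.1% | 49.0% | 5.1 |
| 1.0 | any | 50.0% | 50.0% | 0 |
| 1.1 | 0 | 46.1% | 51.0% | −4.9 |

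**With VEs quoted in Section 7.** At a true VE of 55.4%, p = 0.5, q = 0 and h = 0.8, the rows show 60.4% and 50.4%, a gap of 9.9 points before rounding. At a true VE of 70.7% they show 74.0% and 67.4%, a gap of 6.5. Over both VEs, h from 0.7 to 1.1, p from 0.2 to 0.8 and q of 0 or 0.5, the gap runs from −4.4 to +17.6 points and is zero only at h = 1.

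**Which comparisons remove the artefact** (still no true effect of co-administration)
- Controls with the same influenza status as their recipient: the h terms cancel, both rows return the true VE, and the ratio of risk ratios is 1.
- Same-day against separately influenza-vaccinated recipients: risk ratio = h/h = 1.
- Same-day recipients against recipients without influenza vaccine: risk ratio = (1 − VE_true)·h / (1 − VE_true) = h, so 0.8 at h = 0.8. The planned rows at q = 0 imply the same ratio, (1 − 0.583)/(1 − 0.479) = 0.80. This comparator keeps the selection.

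**The case against.** The strongest reply is that nothing in the protocol shows h differs from 1. At h = 1 the rows agree, and above 1 the sign reverses. This stands: the VEs can differ, and a statement that they will differ, or that co-administration will look beneficial, goes beyond the documents. It does not rescue the analysis, because the plan offers no way to learn h, so an observed difference remains uninterpretable.

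Second, the none-within-a-week row is not a group of non-takers. This also stands. At q = 0.5 the gap halves, and when q exceeds p that row's VE is shifted in the same direction as the co-administered one, so the two rows need not be biased in opposite directions. The equal p across rows is likewise an assumption, since controls are matched by day and their uptake may vary over the season.

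Third, the lack of a stated contrast between rows could be settled in an analysis plan that is not shown. That is fair and is not part of the criticism. The composition of the comparison, however, is fixed in the protocol by the matching lists and the subgroup definition.

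A reader might also infer from Section 9.4 that influenza doses go unrecorded, because the Swedish register "contains information on administered Covid-19 vaccines in Sweden" and the Finnish one is described in similar terms. The documents do not support this. The covariate table names those same registers as the source of influenza vaccination dates, and Section 9.4 does not say that they hold nothing else.

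Finally, Section 9.9 already calls confounding a potential major concern. That is a general statement; for these subgroups it mentions only power.

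**Conclusion.** The point holds in a conditional form. Objective 3 is served only by subgroup VEs in which recipients are selected on influenza vaccination and controls are not. Those VEs can differ when co-administration has no effect, so a difference between them cannot be attributed to co-administration.

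The size is unknown. It is about 10 points at an assumed relative risk of 0.8, about 5 if half of the none-within-a-week group was vaccinated outside the window, zero at relative risk 1, and of opposite sign above 1. These figures rest on assumed values of h, p and q and on equal p in all rows.

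A tempting inference is that the study's VE estimates in general are compromised by this. They are not: the defect arises from the one-sided influenza split and does not touch Objectives 1 and 2. Because it leaves a numbered objective without an interpretable answer, it should be settled before the analysis is run.

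**What to change.** Make one or both of these changes in Sections 9.3 and 9.7.

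(a) Define influenza vaccination for each control relative to the assigned index date, using the same window of one week either side. Add it to the matching for the influenza subgroups, and report the ratio of risk ratios between subgroups with its CI. The window closes before follow-up starts at day 8, so no information from follow-up is used. In the none-within-a-week row, matching on the window removes the artefact fully only if recipients and controls have similar uptake outside it, so tabulate that uptake by arm.

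(b) Add a head-to-head analysis among XBB.1.5 recipients: same-day co-administered against separately influenza-vaccinated, matched on the same covariates and on vaccination date, with the risk ratio and CI. Do not use recipients without influenza vaccine as the comparator.

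Also correct footnote d so that it agrees with the covariate table, and add residual confounding by influenza-vaccine uptake to Section 9.9.

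The cost is one extra matched analysis on register data already in the plan, with fewer pairs and wider CIs. Precision will be limited under (b), because Section 9.9 expects most people to have had both vaccines on the same day, and under (a) where influenza-vaccinated controls are scarce. People who separate the two vaccines may still differ from those who do not, so neither option removes all confounding.

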12. PLANS FOR DISSEMINATING AND COMMUNICATING STUDY RESULTS

Main results expected in the final study report:

- Baseline characteristics-tables, including prior to matching and complementary matching quality diagnostics
- End of week 18 (end of week 24 if possible) cumulative incidence curves-figures for severe Covid-19 outcomes
- Vaccine effectiveness estimates tables for main analysis and influenza co-administration analyses
- Waning vaccine effectiveness figures for severe Covid-19 outcomes

We anticipate one manuscript, and findings will be reported to the general public by institutional press releases upon acceptance in academic peer-review journals or upon uploading to pre-print server (if decided relevant to do so).

We will adhere to the STROBE and ENCEPP guidelines when reporting results and drafting the manuscript(s).

Example of main results table:

	Country-combined measures of association (95% CI) at week 18/24 of follow-up				
	Contributing countries			XBB.1.5-containing vaccine vaccinated	
	Contributing countries	Events/PYRS	XBB.1.5-containing	RD	CVE

			vaccine unvaccinated		
			Events/PYRS		
Covid-19 hospitalization					
All	XX, XX, XX	XXXX/X, XXX, XXX	XXXX/X, XXX, XXX	XX (XX to XX)	XX (XX to XX)
Subgroups					
Male	XX, XX, XX	XXXX/X, XXX, XXX	XXXX/X, XXX, XXX	XX (XX to XX)	XX (XX to XX)
Female	XX, XX, XX	XXXX/X, XXX, XXX	XXXX/X, XXX, XXX	XX (XX to XX)	XX (XX to XX)
<75 years					
≥75 years					
Influenza vaccine co-administered on the same day					
Influenza vaccine administered within -/ +1 week					
No influenza vaccine administered within -/ +1 week					
Covid-19 death					
All					
Subgroups					
Male					
Female					
<75 years					
≥75 years					
Influenza vaccine co-administered on the same day					
Influenza vaccine administered within -/ +1 week					
No influenza vaccine administered within -/ +1 week					

13. References

- [1] Comirnaty: EMA recommends approval of adapted COVID-19 vaccine targeting Omicron XBB.1.5 | European Medicines Agency n.d. <https://www.ema.europa.eu/en/news/comirnaty-ema-recommends-approval-adapted-covid-19-vaccine-targeting-omicron-xbb15> (accessed January 24, 2024).
- [2] Spikevax: EMA recommends approval of adapted COVID-19 vaccine targeting Omicron XBB.1.5 | European Medicines Agency n.d. <https://www.ema.europa.eu/en/news/spikevax-ema-recommends-approval-adapted-covid-19-vaccine-targeting-omicron-xbb15> (accessed January 24, 2024).

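### The third influenza-status level pools recipients vaccinated against influenza more than a week earlier with recipients who had no influenza vaccine, so its VE shows neither a timing nor a receipt effect

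*Protocol*

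**What the plan says.** Objective 3 in protocol section 8 reads: "To assess how the effectiveness of monovalent XBB.1.5-containing Covid-19 vaccines is affected by the coadministration with an influenza vaccine". It does not say what co-administration is to be compared with.

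Section 9.7 (Statistical analysis) plans subgroup analyses by "influenza vaccination status for XBB.1.5-containing Covid-19 vaccine vaccinated", in three levels:

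- Level 1: "1)co-administered on the same date"
- Level 2: "2) received influenza vaccine within 1 weeks before to 1 week after XBB.1.5-containing vaccine dose administration but no on same date"
- Level 3: "3) no influenza vaccine administered within 1 weeks before to 1 week after of XBB.1.5-containing vaccine dose administration"

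The covariate table in section 9.3 has the same three categories, under the label "Influenza vaccination status for season 2023–2024". The example results table in section 12 gives each level its own row for each outcome; the third row is "No influenza vaccine administered within -/ +1 week". On the expected distribution, section 9.9 says only "We expect the majority of the study population will receive both the influenza and the XBB.1.5-containing Covid-19 vaccine on the same day", and that power will probably be lower in those not vaccinated concurrently.

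**The concern.** A recipient can stand in three relations to the influenza vaccine: given on the same day, given on another day, or not given. The protocol's coding recovers the first. It recovers the second only when the gap is 1 to 7 days. The rest of the second is merged with the third, and no section separates them again, although the variable is labelled as a season-wide status.

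Co-administration is one of three study objectives, and section 12 lists its estimates among the main results. A reader who sees the rows for level 1 and level 3 side by side will naturally compare them. People who take no influenza vaccine may differ in background risk from those who take both vaccines. Section 9.7 does not match on influenza vaccination, and section 9.8 itself allows for a healthy vaccinee effect. A difference between the two rows could therefore reflect timing, receipt, or the kind of person in each group. Recipients with widely separated vaccines, who would strengthen the timing comparison, sit where they cannot be seen.

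**Working it through.** **Step 1: definitions.** The protocol states no power, sample size or effect figure for this analysis, so there is none to reproduce. The check starts from the categories in sections 9.3, 9.7 and 12.

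| Influenza vaccine relative to the XBB.1.5 dose | Level |
|---|---|
| Same date | 1 |
| 1 to 7 days before or after | 2 |
| 8 or more days before | 3 |
| None by day 7 after | 3 |

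The last row includes people vaccinated against influenza from day 8 onward. The pooling follows from the definition and needs no assumption.

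**Step 2: what the pooling can do.** Let s be the share of level 3 whose influenza vaccine was more than a week away. With equal background risk in the comparators of the two parts,

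VE(level 3) = 1 − [s × (1 − VE if separated) + (1 − s) × (1 − VE if none)].

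Every VE below, and s, is assumed; none comes from the protocol. VE if separated is taken to be the same at any gap.

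*A. No timing effect: VE 60% with influenza vaccine on any day, 50% with none.* At s = 0.5, VE(level 3) = 1 − (0.5 × 0.40 + 0.5 × 0.50) = 55%, so level 1 minus level 3 is 5 points.

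| s | 0 | 0.25 | 0.5 | 0.75 | 1 |
|---|---|---|---|---|---|
| VE(level 3), % | 50 | 52.5 | 55 | 57.5 | 60 |
| Level 1 − level 3, points | 10 | 7.5 | 5 | 2.5 | 0 |

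*B. As A, but VE with no influenza vaccine is 45% or 70%.* As s goes from 0 to 1, the difference runs from 15 to 0 points, or from −10 to 0.

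*C. A true same-day penalty of 10 points: VE 55% same day, 65% separated, 50% none.* At s = 1/3, VE(level 3) = 1 − (0.35/3 + 2 × 0.50/3) = 55%, so the difference is 0.

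| s | 0 | 1/3 | 0.5 | 1 |
|---|---|---|---|---|
| VE(level 3), % | 50 | 55 | 57.5 | 65 |
| Level 1 − level 3, points | +5 | 0 | −2.5 | −10 |

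**Step 3: the other contrasts.** Under these assumptions level 1 minus level 2 returns the timing effect whatever s is: 0 in A and B, −10 in C. Same day versus more than a week apart, once separated out, does the same. Same day versus none gives 10 points in A and 5 in C, also whatever s is. Only the pooled row depends on the unknown s.

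**The case against.** A reader might infer that the plan uses level 3 as the reference in a same-day-versus-not comparison, and so cannot answer objective 3. The documents do not support that. No level is called a reference, and no such contrast is defined. The plan is a separate VE for each level against XBB.1.5-unvaccinated comparators. Level 1 versus level 2 is already a timing contrast wholly among influenza-vaccinated recipients, and the VE of level 1 describes effectiveness under co-administration. Section 9.9 discloses the lower power elsewhere. All of this stands.

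It is also fair that objective 3 names no alternative. No influenza vaccine close in time is a coherent comparator if the question is interference from concurrent vaccination, and the row label in section 12 says exactly what the row holds. That defends the label. It does not make the row readable as separate administration or as no influenza vaccine.

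Nor do the numbers show a bias of known size created by the pooling. Suppose there is no timing effect, and confounding gives risk ratios of 0.45 with influenza vaccine on any day and 0.65 without. Level 3 then has a risk ratio of 0.61, 0.57 or 0.53 at s = 0.2, 0.4 or 0.6, which is 16, 12 or 8 VE points below the same-day level. At s = 0 the gap is 20 points. The gap comes from the assumed confounding, and pooling here shrinks it. If s is near 0 or 1, level 3 is close to a pure group.

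Finally, the existing window closes before follow-up begins, so the current coding already avoids using follow-up information.

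**Conclusion.** The point holds in a limited form. Level 3 mixes recipients given influenza vaccine more than a week earlier with recipients given none by day 7. Its VE, and any level 1 versus level 3 comparison, cannot be interpreted as an effect of timing or of receipt. The protocol fixes this coding in three places, so it is not a detail left to a statistical analysis plan.

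The size and direction of any distortion are unknown: the protocol gives no share for level 2, level 3 or the parts of level 3. The ranges in the working show what is possible under assumed values and estimate nothing. That level 2 will be small is a reasonable expectation, not a documented figure. The consequence is confined to one subgroup row per outcome and to how objective 3 is read from it.

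**What to change.** In sections 9.3, 9.7 and 12, split level 3 using the vaccination dates from which the variable is already built:

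- **3a:** influenza vaccine recorded in the 2023-24 season, more than 7 days before the index date.
- **3b:** no influenza vaccine recorded in the season up to day 7 after the index date.

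Label the variable as status at start of follow-up, because some people in 3b may be vaccinated later. Classification then closes at day 7, before follow-up starts on day 8, and uses no follow-up information. Define the start of the season. Note that Finland's definition in section 9.3 names only two influenza products, so a recipient of any other product could be coded as having none.

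State that same-day versus separate-day (level 2 plus 3a) is the timing contrast for objective 3, and report 3b separately. The pooled row can be kept alongside.

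The cost is a few lines of wording and code, and one more row per outcome (two if the pooled row stays). The split rows are smaller and have wider intervals. Same-day and separate-day recipients may still differ in ways the matching does not capture, so residual confounding remains in the timing contrast.
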